#### PFIZER CONFIDENTIAL

CT24-WI-GL02-RF02 6.0 Non-Interventional Study Protocol Template For Secondary Data Collection Study Page 17 of 53 Exclusion criteria rationale:

- Individuals with evidence of PCV13 vaccination prior to the index date were excluded because the individual would not be eligible to receive a PCV13 vaccine during the study period
- Individuals with evidence of PPSV23 vaccination in the 365 days prior to the index date were excluded because PPSV23 receipt within 365 days prior to PCV13 receipt could result in hyporesponsiveness to the PCV13 vaccine. In addition, the CDC ACIP PCV13 receive a dose of PCV13 if the individual had not previously received a pneumococcal vaccine or if the individual received PPSV23 ≥1 year prior. This exclusion criterion was included to align with the CDC ACIP recommendations at the start of the study period.
- The CDC ACIP recommended PCV13 for adults age ≥19 years with a high-risk condition for pneumonia on October 12, 2012. Individuals with ≥1 diagnosis code for a pneumonia high-risk condition in the 365 days prior or evidence of iatrogenic immunosuppression in the 6 months prior to index were excluded because these individuals were eligible to receive PCV13 prior to turning age 65 years and before being eligible to enroll in Medicare health insurance. Since records of vaccination prior to enrolling in Medicare are not available in the database, these individuals were excluded to reduce the risk of misclassifying PCV13 vaccination status.
- Individuals with a pneumonia diagnosis code in the hospital setting in the 365 days prior to the index date were excluded because recent history of severe pneumonia increases the risk of a future diagnosis of pneumonia. Pneumonia is the hypothesized mediator for the impact of PCV13 on risk of MACE. Excluding these individuals equalizes this risk for the PCV13 vaccinated and PCV13 unvaccinated cohorts.
- Individuals with a MACE diagnosis code in the hospital, SNF, and LTCF setting the 365 days prior to the index date were excluded because recent history of an acute MACE event increases the risk of a future MACE event. Excluding these individuals equalizes this risk for the PCV13 vaccinated and PCV13 unvaccinated cohorts.
- Individuals with Medicare Part C enrollment between September 14, 2014 and the index date were excluded because the individual would have been eligible to receive PCV13, but any vaccination records during enrollment in Medicare Part C would not be included in the individual's Medicare FFS records. As such, these individuals were excluded to reduce the risk of misclassifying PCV13 vaccination status.
- PCV13 vaccinated individuals with a pneumonia diagnosis code in the hospital setting or a MACE diagnosis code in the hospital, SNF, or LTCF setting in the 13 days after first PCV13 vaccination because the vaccine is not considered to be fully effective until 14 days following vaccination.

Exclusion criteria: Sample size impact

• Approximately 25 million individuals are estimated to be eligible for inclusion in the study. As such, these exclusion criteria do not substantially impact the ability to meet the minimum sample size required for this study. Please refer to **Section 9.5** for additional information on the minimum sample size required for this study.

### PFIZER CONFIDENTIAL

CT24-WI-GL02-RF02 6.0 Non-Interventional Study Protocol Template For Secondary Data Collection Study Page 18 of 53

# 9.2.1. Inclusion Criteria

Patients must meet all of the following inclusion criteria as of the index date to have the respective time segment included in the study:

- 1. Enrolled in Medicare FFS Parts A and B as of September 14, 2014 (date of PCV13 ≥65 recommendation in the Morbidity and Mortality Weekly Report (MMWR))
- 2. Aged ≥65 years as of September 14, 2014
- 3. Continuous enrollment in Medicare FFS Parts A and B for at least 6 months prior to the index date

[figure not shown]
# 9.2.2. Exclusion Criteria

Patients meeting any of the following criteria as of the index date will not have the respective time segment included in the study:

- 1. Evidence of PCV13 vaccination prior to the index date
- 2. Evidence of PPSV23 vaccination in the 365 days prior to the index datea
- 3.  $\geq 1$  diagnosis code for a high-risk condition in the 365 days prior to the index datea
- 4. Evidence of iatrogenic immunosuppression in the 6 months prior to the index date
- 5. Pneumonia diagnosis code in the hospital setting in the 365 days prior to the index datea
- 6. MACE diagnosis code in the hospital, SNF, or LTCF setting in the 365 days prior to the index datea
- 7. Medicare Part C enrollment between September 14, 2014 and the index date
- 8. PCV13 vaccinated individuals with a pneumonia diagnosis code in the hospital setting or a MACE diagnosis code in the hospital, SNF, or LTCF setting in the 13 days after first PCV13 vaccination

a. For adults with  $\geq 6$  months, but less than 365 days of prior continuous enrollment, the exclusion criteria will be evaluated during the continuous enrollment period that the adult has available.

#### Figure 1. Illustrative Timeline

- 1. Continuous enrollment (CE)
- 2. Vaccination (vx); diagnosis (dx); skilled nursing facility (SNF); long-term care facility (LTCF)
- 3. Excludes vaccinated time segments where the adult had a pneumonia hospitalization or a hospital, SNF, LTCF MACE dx in the 13 days after PCV13 vaccination

# 9.3. Variables

## 9.3.1. Exposure

### Table 1.Exposure Variable

Variable	Role	Operational definition	Measurement period
PCV13 vaccination	Exposure	One claim (Current procedural terminology® [CPT] or National Drug Codes [NDC]) for PCV13 vaccination. CPT and NDC codes for PCV13 vaccination are listed in Appendix Table 1.	Follow-up

# 9.3.2. Outcomes

# Table 2.Outcome Variables

Variable	Role	Operational definition	Measurement period
Any MACE	Outcome	
 
≥1 International Classification of Diseases, Ninth Revision, Clinical Modification (ICD-9-CM) or International Classification of Diseases, 10th revision, Clinical Modification (ICD-10-CM) diagnosis code for myocardial infarction, stroke, or heart failure in the hospital, SNF, or LTCF setting.
 
Analyses include first event only and the code must occur one of the following time periods:
 
1. ≥0 days after the unvaccinated index date and before the minimum date of censoring for the unvaccinated time segment
 
2. ≥14 days after the vaccinated index date and before the minim date of censoring for the vaccinated time segment.
 
	Follow-up

PFIZER CONFIDENTIAL

CT24-WI-GL02-RF02 6.0 Non-Interventional Study Protocol Template For Secondary Data Collection Study Page 21 of 53

		ICD-9-CM or ICD-10-CM codes are listed in Appendix Table 2.	
Myocardial infarction	Outcome	≥1 ICD-9-CM or ICD-10-CM diagnosis code for myocardial infarction in the hospital, SNF, or LTCF setting.	Follow-up
		Analyses include first event only and the code must occur one of the following time periods:	
		
 
≥0 days after the unvaccinated index date and before the minimum date of censoring for the unvaccinated time segment
 
	
		
 
≥14 days after the vaccinated index date and before the minim date of censoring for the vaccinated time segment.
 
	
		ICD-9-CM or ICD-10-CM codes are listed in Appendix Table 2.	
Stroke	Outcome	≥1 ICD-9-CM or ICD-10-CM diagnosis code for ischemic stroke in the hospital, SNF, or LTCF setting.	Follow-up
		Analyses include first event only and the code must occur one of the following time periods:	
		
 
≥0 days after the unvaccinated index date and before the minimum date of censoring for the unvaccinated time segment
 
	
		
 
≥14 days after the vaccinated index date and before the minim date of censoring for the vaccinated time segment.
 
	
		ICD-9-CM or ICD-10-CM codes are listed in Appendix Table 2.	
Stroke sensitivity	Outcome	≥1 ICD-9-CM or ICD-10-CM diagnosis code for ischemic or hemorrhagic stroke in the hospital, SNF, or LTCF setting.	Follow-up

CT24-WI-GL02-RF02 6.0 Non-Interventional Study Protocol Template For Secondary Data Collection Study Page 22 of 53

		
 
Analyses include first event only and the code must occur one of the following time periods:
 
1. ≥0 days after the unvaccinated index date and before the minimum date of censoring for the unvaccinated time segment
 
2. ≥14 days after the vaccinated index date and before the minimum date of censoring for the vaccinated time segment.
 
ICD-9-CM or ICD-10-CM codes are listed in Appendix Table 2.
 
	
Heart failure	Outcome	
 
≥1 ICD-9-CM or ICD-10-CM diagnosis code for heart failure in the SNF, or LTCF setting.
 
Analyses include first event only and the code must occur one of the following time periods: 
 
≥0 days after the unvaccinated index date and before the minimum date of censoring for the unvaccinated time segment
 
≥14 days after the vaccinated index date and before the minimum date of censoring for the vaccinated time segment.
 
 
 
ICD-9-CM or ICD-10-CM codes are listed in Appendix Table 2.
 
	Follow-up
Cataract surgery	Negative control outcome	≥1 International Classification of Diseases, Ninth Revision, Procedure Coding System (ICD-9-PCS), International Classification of Diseases, Tenth Revision, Procedure Coding System (ICD-10-PCS), CPT, or Healthcare Common Procedure Coding System (HCPCS) code for cataract surgery in any setting.	Follow-up

CT24-WI-GL02-RF02 6.0 Non-Interventional Study Protocol Template For Secondary Data Collection Study Page 23 of 53

		
 
Analyses include first event only and the code must occur one of the following time periods:
 
1. ≥0 days after the unvaccinated index date and before the minimum date of censoring for the unvaccinated time segment
 
2. ≥14 days after the vaccinated index date and before the minimum date of censoring for the vaccinated time segment.
 
	
Lipoma	Negative control outcome	
 
≥1 ICD-9-CM or ICD-10-CM diagnosis code for lipoma in any setting.
 
Analyses include first event only and the code must occur one of the following time periods: 
 
≥0 days after the unvaccinated index date and before the minimum date of censoring for the unvaccinated time segment
 
≥14 days after the vaccinated index date and before the minimum date of censoring for the vaccinated time segment.
 
 
 
	Follow-up
Follow-up time	Outcome descriptive	Unvaccinated follow-up time is measured from the unvaccinated index date through minimum date of censoring. Vaccinated follow-up time is measured from 14 days after first PCV13 vaccination through the minimum date of censoring. Mean, standard deviation (SD), median (Q1-Q3), minimum, and maximum, will also be summarized for the length of follow-up in each group.	Follow-up

PFIZER CONFIDENTIAL CT24-WI-GL02-RF02 6.0 Non-Interventional Study Protocol Template For Secondary Data Collection Study Page 24 of 53

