# 8. RESEARCH QUESTION AND OBJECTIVES

Research question:

Is prior receipt of PCV13 associated with reduced risk of major adverse cardiovascular events (MACE) outcomes in adults aged  $\geq 65$  years?

The primary objective of this study is to:

1. Evaluate the effect of PCV13 receipt on the risk of major adverse cardiovascular events (MACE) at 1 and 3 years of follow-up among adults aged ≥65 years

The secondary objectives of this study are to:

PFIZER CONFIDENTIAL CT24-WI-GL02-RF02 6.0 Non-Interventional Study Protocol Template For Secondary Data Collection Study Page 15 of 53

- 1. Evaluate the effect of PCV13 receipt on the risk of myocardial infarction at 1 and 3 years of follow-up among adults aged ≥65 years
- 2. Evaluate the effect of PCV13 receipt on the risk of stroke at 1 and 3 years of follow-up among adults aged ≥65 years
- 3. Evaluate the effect of PCV13 receipt on the risk of hospitalization due to heart failure at 1 and 3 years of follow-up among adults aged ≥65 years
- 4. Examine the degree to which CAP mediates the relationship between PCV13 receipt and MACE at 1 year of follow-up among adults aged >=65 years

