Outpatient heart failure	Patient characteristics	Any code for heart failure in the outpatient setting in the 365 days prior to the index date.	Baseline
Coronary artery disease (CAD)	Patient characteristics	Any code (any setting) for coronary artery disease (CAD) in the 365 days prior to the index date.	Baseline
Hypertension	Patient characteristics	Any code (any setting) for hypertension in the 365 days prior to the index date.	Baseline
Valvular heart disease	Patient characteristics	Any code (any setting) for valvular heart disease in the 365 days prior to the index date.	Baseline
Unstable angina	Patient characteristics	Any code (any setting) for unstable angina in the 365 days prior to the index date.	Baseline

CT24-WI-GL02-RF02 6.0 Non-Interventional Study Protocol Template For Secondary Data Collection Study Page 28 of 53

Stable angina	Patient characteristics	Any code (any setting) for stable angina in the 365 days prior to the index date.	Baseline
Aortic aneurysm and dissection	Patient characteristics	Any code (any setting) for aortic aneurysm and dissection in the 365 days prior to the index date.	Baseline
Arrhythmia	Patient characteristics	Any code (any setting) for arrhythmia in the 365 days prior to the index date.	Baseline
Atrial fibrillation	Patient characteristics	Any code (any setting) for atrial fibrillation in the 365 days prior to the index date.	Baseline
Cardiomyopathy	Patient characteristics	Any code (any setting) for cardiomyopathy in the 365 days prior to the index date.	Baseline
Peripheral arterial disease (PAD)	Patient characteristics	Any code (any setting) for peripheral arterial disease (PAD) in the 365 days prior to index	Baseline
Pulmonary hypertension	Patient characteristics	Any code (any setting) for pulmonary hypertension in the 365 days prior to the index date.	Baseline
Rheumatic heart disease	Patient characteristics	Any code (any setting) for rheumatic heart disease in the 365 days prior to the index date.	Baseline
Congenital heart defects	Patient characteristics	Any code (any setting) for congenital heart defects in the 365 days prior to the index date.	Baseline
High cholesterol	Patient characteristics	Any code (any setting) for high cholesterol in the 365 days prior to the index date.	Baseline
High triglycerides	Patient characteristics	Any code (any setting) for high triglycerides in the 365 days prior to the index date.	Baseline

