ICD-9-CM	410.41	Acute myocardial infarction of other inferior wall, initial episode of care
ICD-9-CM	410.51	Acute myocardial infarction of other lateral wall, initial episode of care
ICD-9-CM	410.61	True posterior wall infarction, initial episode of care
ICD-9-CM	410.71	Subendocardial infarction, initial episode of care
ICD-9-CM	410.81	Acute myocardial infarction of other specified sites, initial episode of care
ICD-9-CM	410.91	Acute myocardial infarction of unspecified site, initial episode of care
Heart failure		Teate injocardiar infaction of anspectified site, infaar episode of care
ICD-10-CM	150	Heart failure
ICD-10-CM	150.1	Left ventricular failure
ICD-10-CM	150.2	Systolic (congestive) heart failure
ICD-10-CM	150.20	Unspecified systolic (congestive) heart failure
ICD-10-CM	150.20	Acute systolic (congestive) heart failure
ICD-10-CM	150.22	Chronic systolic (congestive) heart failure
ICD-10-CM	150.23	Acute on chronic systolic (congestive) heart failure
ICD-10-CM	150.3	Diastolic (congestive) heart failure

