ICD-10-CM       150.32       Chronic diastolic (congestive) heart failure         ICD-10-CM       150.4       Combined systolic (congestive) and diastolic (congestive) heart failure         ICD-10-CM       150.40       Unspecified combined systolic (congestive) and diastolic (congestive) heart failure         ICD-10-CM       150.41       Acute combined systolic (congestive) and diastolic (congestive) heart failure         ICD-10-CM       150.42       Chronic combined systolic (congestive) and diastolic (congestive) heart failure         ICD-10-CM       150.43       Acute on chronic ombined systolic (congestive) and diastolic (congestive) heart failure         ICD-10-CM       150.81       Right heart failure       ICD-10-CM         ICD-10-CM       150.81       Right heart failure       ICD-10-CM         ICD-10-CM       150.811       Acute on chronic right heart failure       ICD-10-CM         ICD-10-CM       150.812       Chronic right heart failure       ICD-10-CM         ICD-10-CM       150.813       Acute on chronic right heart failure       ICD-10-CM         ICD-10-CM       150.814       Right heart failure       ICD-10-CM       I50.82         ICD-10-CM       150.83       High output heart failure       ICD-10-CM       I50.84       End stage heart failure         ICD-10-CM       150.84       End stage heart fai	ICD-10-CM	150.30	Unspecified diastolic (congestive) heart failure

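### Any MACE accepts chronic-only and unspecified heart failure codes on any facility claim, so known background disease can be recorded as a first event

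*Protocol*

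**What the plan says.** Protocol section 9.3.2, Table 2, defines Any MACE as one or more "diagnosis code for myocardial infarction, stroke, or heart failure in the hospital, SNF, or LTCF setting". It adds that "Analyses include first event only and the code must occur one of the following time periods", and then gives the two follow-up windows. The row sets no diagnosis position, acuity or reason for the stay.

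The heart failure list in Appendix Table 2 includes "Chronic systolic (congestive) heart failure" (I50.22) and "Chronic diastolic (congestive) heart failure" (I50.32). It also holds I50.42, I50.812, 428.22, 428.32 and 428.42, and the unspecified codes I50.9, 428.0 and 428.9.

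Outpatient heart failure is a baseline covariate in Table 5: "Any code for heart failure in the outpatient setting in the 365 days prior to the index date". It is not an exclusion. The only exclusion in section 9.2.2 that bears on earlier heart failure is criterion 6, a MACE code from a hospital, SNF or LTCF in the 365 days before index.

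Secondary objective 3 (section 8) concerns the "risk of hospitalization due to heart failure at 1 and 3 years of follow-up". The stand-alone heart failure row of Table 2 reads "diagnosis code for heart failure in the SNF, or LTCF setting" and does not list the hospital.

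**The concern.** A chronic heart failure code describes a condition the patient already has. When such a patient is admitted for a fracture, an operation or a pneumonia and the code is recorded on the claim, the Any MACE rule is met. For eligible patients with known heart failure, part of the primary endpoint then measures use of facility care.

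Two distortions follow. PCV13 is expected to work by reducing pneumonia (section 7), so a prevented pneumonia stay also removes the heart failure code that would have come with it. That looks like prevented MACE even if nothing cardiovascular changed. Codes recorded during stays unrelated to pneumonia do the opposite and add events that the vaccine cannot affect.

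Nothing planned would show either effect. The three sensitivity analyses in section 9.7 vary the competing-risk model, the stroke definition and the CAP setting. The negative control outcomes, cataract surgery and lipoma, are counted in any setting and so do not track facility stays.

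**Working it through.** **Reading the definition against the rest of the protocol**

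1. *Who can enter.* Criterion 6 removes patients with a facility MACE code in the prior 365 days. Two groups remain: those whose heart failure is coded only in outpatient care, and those whose last facility code is older than 365 days.
2. *What makes them a case.* One listed heart failure code on a hospital, SNF or LTCF claim is enough, and chronic-only and unspecified codes are listed.
3. *What the protocol says it wants.* Objective 3 requires that heart failure be the cause of the hospitalization. The rationale for criterion 6 in section 9.2 speaks of acute events. No part of the Any MACE row carries either condition.
4. *Contrast within the same appendix.* ICD-9 MI codes are restricted, for example "Acute myocardial infarction of other inferior wall, initial episode of care". Heart failure has no such restriction.
5. *The stand-alone row.* It omits the hospital, so as written a hospital admission for heart failure would not count there. It conflicts with both objective 3 and the Any MACE row.

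**The plan's own figures**

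Inputs from section 9.5: 5-year overall event probability 21.2%, HR 0.85, allocation 2:3. Solving 0.4(1 − e^(−0.85·5L)) + 0.6(1 − e^(−5L)) = 0.212 gives L = 0.0507, as stated. A Lakatos log-rank calculation (two-sided 0.05, 80% power, 1 year) gives 27,571 against the stated 27,520. The sample size is sound and the point does not depend on it.

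**Direction**

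Let f be the share of control-arm events that are incidental codes, h the vaccine's hazard ratio on those codes, and H its hazard ratio on genuine events. Approximately:

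observed HR = H(1 − f) + f·h

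- If h = 1 and H = 0.85, the observed HR is 0.85(1 − f) + f. With f = 0.1 it is 0.865, and with f = 0.3 it is 0.895: dilution.
- If H = 1 (no cardiovascular effect) and h < 1 because pneumonia stays are prevented, the observed HR is 1 − f(1 − h), which is below 1: a spurious benefit.
- If H = 0.85, the observed HR lies above 0.85 when h > 0.85 and below it when h < 0.85.

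The protocol gives neither f nor h.

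**How large f might be (assumptions only)**

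Assume that 5% to 10% have outpatient-known heart failure at baseline and that 30% to 50% a year have a facility stay carrying the code. Each person counts once per segment, so over 5 years:

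- 5% × (1 − e^(−1.5)) = 3.9 points, and 3.9/21.2 = 18%
- 10% × (1 − e^(−2.5)) = 9.2 points, and 9.2/21.2 = 43%
- if every member of a 10% group were counted: 10/21.2 = 47%

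These shares are of overall rather than control-arm events. They treat every such stay as incidental, although some would be genuine decompensation. They show that f need not be trivial, but they do not estimate it.

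**The case against.** Much of the other side's case stands, and it limits the point.

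- *Diagnosis position.* The protocol does not say that a code in any position counts; that is inferred from a definition with no position rule. The SAP is not shown and might add one. However, section 9.7 says major changes to primary endpoint definitions go into a protocol amendment, and a position rule would be such a change.
- *Any admission.* A reader might infer that every admission of a heart failure patient becomes MACE. It does not. A heart failure code must be on the claim, and patients facility-coded in the prior 365 days, who may be among the likeliest to be readmitted, are excluded.
- *Size.* A reader might multiply 10% by 50%, obtain 5.0 per 100 person-years, set it beside the planning hazard of 5.07, and conclude that half or more of the events are incidental, with an HR of 0.925 or worse. That ignores first-event counting. On the same inputs the 5-year share is at most 43%. The 1-year share could be higher, but no 1-year event rate is given.
- *Mediation.* A reader might call the CAP mediation result circular. CAP must occur before censoring (Table 3) and the outcome itself censors (Table 4). Whether one stay can supply both depends on how ties are dated, which the protocol does not settle.
- *Principal diagnosis for all MACE.* This would be a poor remedy. Section 7 describes cardiovascular complications during and after CAP. An MI, stroke or acute heart failure complicating a pneumonia admission may carry pneumonia as principal diagnosis, so the rule would remove the very pathway under study.
- *Adjustment.* Outpatient heart failure, cardiomyopathy, prior hospitalizations and SNF stay are covariates. They help to balance the groups, but they do not turn a background code into an event.

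**Conclusion.** The point holds for the heart failure component. As written, Any MACE lets a chronic-only or unspecified heart failure code on a facility claim count as a first event in patients whose heart failure predates follow-up. This matches neither objective 3 nor the protocol's own reference to acute events. It affects the primary endpoint, and no planned analysis would reveal it.

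Neither the direction nor the size of the net bias can be fixed from the protocol, because dilution and spurious benefit pull opposite ways. The shares worked out above rest on assumed prevalence and stay rates and should not be quoted as estimates. With about 25 million eligible, the harm lies in bias and interpretation rather than power. The conclusion rests on reading Table 2 as a complete definition. It does not extend to MI or stroke. For the stand-alone heart failure row, the first defect is the missing hospital setting.

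**What to change.** By protocol amendment, for both the heart failure component of Any MACE and the heart failure outcome:

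- Count an inpatient stay only if it carries an acute or acute-on-chronic heart failure code in any position, or any listed heart failure code as principal diagnosis.
- Do not let chronic-only or unspecified secondary codes qualify, nor SNF or LTCF heart failure codes standing alone.
- Leave the MI and stroke code rules unchanged, so that events complicating a pneumonia admission still count.
- Keep the present broad definition as a sensitivity analysis. A difference between the two results would show how much the background codes matter.
- Reconcile the settings in the stand-alone heart failure row with objective 3 and the Any MACE row.
- State which code list exclusion criteria 6 and 8 then use, since both refer to MACE codes.

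The cost is revised wording and code flags, assuming the claims files carry diagnosis position. There will be fewer heart failure events, and some sensitivity is lost where acute heart failure is coded as unspecified in a secondary position. The study can afford this: 25,000,000/36,485 is about 685 times the largest sample size in Table 6.
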